4.2 TEA

4.2.1 - All patients assigned to TEA will have thoracic epidurals placed preoperatively in either the holding area or in the operating room according to current institutional protocol. Epidural catheters will be placed between the Thoracic 5th-Thoracic 10th interspinous levels using standard technique according to institutional practices. All epidural catheters will be tested for correct placement and level of block documented and secured as is currently practiced. The epidural will be initially dosed according to current practices with hydromorphone (10 mcg/kg for pts 65 yrs or younger and 5 mcg/kg for pts > 65yrs) after induction of anesthesia. Standard epidural solutions are: Hydromorphone (10 mcg/ml for pts 65yrs or younger and 5 mcg/ml for pts > 65yrs) and Bupivacaine (0.075%) at 10 ml/hr continuous infusion and a 3ml every 10 minutes demand dosing, and a 5ml every 3 hours clinician bolus as needed for additional pain control (Appendix B). Fentanyl with Bupivacaine

will be secondary alternatives. Adjunctive use of oral, rectal, or intravenous non-narcotic analgesics (acetaminophen, non-steriodals, etc.) will be utilized at the discretion of Acute Pain Service and/or Primary Surgical Team. Epidural catheters will remain in place a maximum of 7 days postoperatively. Epidural catheters will be removed once patients are successfully tolerating a full diet or tube feeds and are transitioned to oral/enteral analgesics. Indwelling urinary catheters will be removed after TEA removal per current policy.

4.2.2 - Patients whose TEA's are not functioning or not providing adequate analgesia will be considered for IVPCA as an alternative analgesic regimen (patient crossover).

4.2.3 - Further drug information can be found in the MDACC formulary and the FDA approved package inserts of the medications as they are all commercially available.

5. Treatment Plan – Perioperative Monitoring

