8.0 Statistical Considerations

8.1 Methodology

- This is a two-arm randomized non-blinded study whose primary objectives are to compare postoperative pain scores and quality of life (QOL) scores in patients undergoing liver and/or pancreatic resection between those receiving TEA versus IVPCA. Eligible patients will be randomized in a 3:1 allocation ratio to the treatment group of TEA or IVPCA group (to represent our current institutional practice as well as to allow a more accurate determination of overall TEA failures and complications). Randomization will be stratified by the resection type (liver or pancreatic - 1:1). The randomization will be conducted by the CORE prior to surgery and after consent and registration. Pain will be assessed using a numeric/visual pain score at various timepoints. The pain scores will be averaged for each patient and be compared between TEA and IVPCA groups at specific time points as follows: pain scores for the first 6 hours after surgery, pain scores for the next 18hrs after surgery, pain scores for each subsequent 24hr period after surgery until postoperative day #5 or epidural removed, whichever occurs first. QOL will be assessed pre- and postoperatively using SF-8 and SF-36v2. These validated instruments will score 8 domains that will be reduced to two summary measures scales, Physical Component Summary (PCS) and the Mental Health Component Summary (MCS). Scoring will be performed utilizing proprietary certified scoring software from the vendor. QOL scores will be calculated and compared between the two groups of patients.
- Categorical data will be tabulated with frequency and percentages, and continuous variables will be summarized using descriptive statistics mean, standard deviation, median and range. The primary

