8.2 Sample Size

- A total of 200 liver and pancreatic resection patients will be enrolled in order to achieve 140 evaluable patients. As these surgical procedures are for resection of malignancy, a proportion of patients will be identified with unresectable or metastatic disease at the time of planned resection either during initial laparoscopy or after open exploration. Those patients deemed unresectable at laparoscopy will not undergo open exploration, and thus, will be inevaluable for postoperative pain due to differences in incision type. Furthermore those patients that do undergo an open exploration but are deemed unresectable due to local or metastatic disease found intraoperatively will have markedly different prognoses compared to those that have a successful resection, which may bias their response to pain and quality of recovery and bias the questionnaire responses. Based on previous work at our and other institutions, it is expected that up to 30% of patients will not be evaluable due to various reasons, including ineligibility, patient withdrawal from the study, unresectable disease, and failure to complete or inaccurate completion of questionnaires. Based on historical information, if the difference in mean pain score between the two evaluable treatment groups of patients is 1 and the common standard deviation is 1.5, with a total of 140 evaluable patients (105 in TEA group and 35 in IVPCA group), the study will yield a 92% power to detect the difference, using a two-sample t-test at a two-sided significance level of 0.05. Furthermore, the study will have a 99% power to detect a difference of 10 in QOL score with a corresponding standard deviation of 9 using a two-sided Student's t-test with a type I error of 0.05. All statistical analyses will be performed with an intent to

treat methodology, including those patients who cross over between treatment groups.

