This study will be monitored by The Data Safety and Monitoring Board (DSMB), through routine reviews and/or institutional audits. The DSMB reports to the President, or his designee, as the on-campus representative of The University of Texas Board of Regents. It oversees the data and patient safety issues for randomized Phase III clinical trials that originate at UTMDACC; that are coordinated or analyzed by UTMDACC and are not being monitored by any other DSMB; or has been designated as the DSMB for any trial at the request of the IRB, the CRC, or institution. The primary objectives of the DSMB are to ensure that patients' rights pertaining to participation in a research study are protected, and that patients' interests are prioritized over the interests of the scientific investigation. Responsibilities include:

- (a) **Review interim analyses of outcome data after 60 evaluable patients are enrolled (prepared by the study statistician or other responsible person at the time points defined in the study) approved by the IRB and additional time points as determined by the DSMB, and to**

recommend, if necessary, whether the study needs to be changed or terminated based on these analyses;

- (b) Determine whether, and to whom, outcome results should be released prior to the reporting of study results;**
- (c) Review interim toxicity data and efficacy of treatment;**
- (d) Review major research modifications proposed by the investigator or appropriate study committee prior to implementation (e.g., termination, dropping an arm based on toxicity results from the study or results of other studies, increasing target sample size).**

The DSMB consists of not more than 15 members (including the Chair) as recommended by the President, or his designee, for each fiscal year. The committee includes physicians, statisticians and lay member(s), and will be selected based on their experience, reputation for objectivity, absence of conflicts of interest (or the appearance of the same), and knowledge of good clinical trial methodology. The committee meets 5 times per year, and may schedule additional meetings if needed.

11. Confidentiality

- This study will be conducted in accordance with all applicable privacy laws, rules and regulations. The Principal Investigator will take steps to guard against any loss of confidentiality. Only the Principal Investigator, Study Co-Chairs, and the authorized research team will have access to the identifiable information from this study.

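### Epidural complications have no by-receipt population: the blanket intent-to-treat rule books crossover-catheter harms to IVPCA, and 8.2 leaves the TEA denominator at anything from about 105 to 150

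*Combined protocol and SAP*

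**What the plan says.** **Purpose.** Section 8.1 gives as one reason for 3:1 allocation "to allow a more accurate determination of overall TEA failures and complications". Section 7.2.1 lists epidural complications among the secondary endpoints, and the hypothesis at the end of 2.8 includes the absence of significant epidural-related risk.

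**Exposure.** Section 4.2.1: "All patients assigned to TEA will have thoracic epidurals placed preoperatively". Section 4.1.2 allows an IVPCA patient with a failing pump or inadequate relief to be considered for a postoperative epidural. Section 4.2.2 allows the reverse switch.

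**Analysis rule.** The last sentence of the first paragraph of 8.2 covers all statistical analyses and prescribes intent to "treat methodology, including those patients who cross over between treatment groups".

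**Evaluable set.** The same paragraph begins: "A total of 200 liver and pancreatic resection patients will be enrolled in order to achieve 140 evaluable patients". It then says "it is expected that up to 30% of patients will not be evaluable due to various reasons", and the reasons named are "ineligibility, patient withdrawal from the study, unresectable disease, and failure to complete or inaccurate completion of questionnaires". The evaluable total is split into 105 TEA and 35 IVPCA patients.

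**Monitoring.** Section 10(a) asks the DSMB to "Review interim analyses of outcome data after 60 evaluable patients are enrolled"; 10(c) separately asks it to review interim toxicity.

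No section defines a safety set, a set by catheter received, or a denominator for epidural complications. Section 6.1 labels the daily epidural site check as TEA only, without saying whether that means assigned or received.

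**The concern.** A catheter complication can occur only in someone who had a catheter, or an attempt at one. Its natural denominator is the patients exposed. The plan's one explicit rule assigns it by randomised arm instead. An epidural harm in an IVPCA patient who crossed over would then count against the non-epidural arm. It would be missing from the TEA rate that the allocation ratio was partly chosen to measure. Section 2.8 notes that coagulation disorders occur after hepatic resection even when preoperative tests are normal, so catheters placed after surgery should not be lost within another arm's total.

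The second difficulty is the denominator. A TEA patient found unresectable at operation has already had the catheter. That patient is not evaluable under 8.2, yet remains in an intent-to-treat set of all randomised patients. Two analysts could use different denominators and both claim to follow the plan.

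**Working it through.** **1. The plan's own figures.** With 105 and 35 patients, a difference of 1, an SD of 1.5 and two-sided alpha of 0.05, noncentral-t power is 92.4%, against 92% stated. Enrolment is 140 / 0.70 = 200, as stated. The point changes neither. The plan states no complication rate or precision target, so there is none to reproduce.

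**2. The two possible TEA denominators.**
- Randomised to TEA: 200 × 3/4 = 150.
- Evaluable in TEA: 140 × 3/4 = 105.
- Difference: 150 − 105 = 45. This is a ceiling on exposed patients lost, because some ineligible or withdrawn patients may never have reached catheter placement.

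**3. Precision if the evaluable set were used.** With zero events the exact upper limit is 1 − a^(1/n), where a = 0.05 for the one-sided 95% limit and a = 0.025 for the two-sided 95% limit.

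| n | One-sided | Two-sided |
|---|---|---|
| 105 | 1 − 0.05^(1/105) = 2.8% | 1 − 0.025^(1/105) = 3.5% |
| 150 | 1 − 0.05^(1/150) = 2.0% | 1 − 0.025^(1/150) = 2.4% |

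At an assumed 10% rate the approximate 95% half-width is 1.96 × √(0.10 × 0.90 / 105) = 5.7 points, against 1.96 × √(0.10 × 0.90 / 150) = 4.8 points.

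**4. Bias if the evaluable set were used.** Assume a 10% rate in the 105 evaluable patients, all 45 others exposed, and a rate r in those 45. The rate in all exposed patients is (105 × 0.10 + 45 × r) / 150.
- r = 0: 10.5 / 150 = 7%
- r = 10%: 15 / 150 = 10%
- r = 20%: 19.5 / 150 = 13%

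The evaluable figure of 10% could therefore be 3 points too high, correct, or 3 points too low. The documents do not say which.

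**5. Crossover catheters.** The documents give no crossover share. Assume 0 to 30% of the 35 evaluable IVPCA patients, so up to 35 × 0.30 = 10.5 catheters, and a complication rate per crossover catheter equal to an assumed 10% in TEA or twice that.
- Events placed under IVPCA: from 0 to 10.5 × 0.10 = 1.05 at equal risk, or to 10.5 × 0.20 = 2.1 at double risk.
- Apparent IVPCA rate at the top of the range: 2.1 / 35 = 6%.
- Rate over all catheters at the top of the range: (105 × 0.10 + 2.1) / (105 + 10.5) = 12.6 / 115.5 = 10.9%, against 10.0% by assigned arm.

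The effect on the TEA rate is 0 to 0.9 points. The more visible effect is about 0 to 2 epidural events in a column of 35 patients.

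**The case against.** Several stronger readings are tempting, and the case against them is good.

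- **Complications are to be counted only in evaluable patients.** A reader might infer this from 8.2, but nothing there says so. The reasons given for excluding unresectable patients concern pain, quality of recovery and questionnaire responses, and the 105/35 split feeds a pain-score t-test. Strict intent to treat would keep about 150 TEA patients. What stands is that the two concepts sit in one paragraph and are not reconciled.
- **The rules make TEA look safer.** This is not established. Section 2.8 ties the coagulation concern partly to hepatic resection, which unresectable patients do not undergo, so leaving them out could raise the TEA rate. Step 4 shows that the bias can be zero or go either way. Under 4.2.2, opioid complications after a switch from TEA to IVPCA are counted against TEA, which works in the opposite direction.
- **The DSMB sees only evaluable patients.** The 60 evaluable patients in 10(a) set when a review happens. The toxicity review in 10(c) carries no such restriction.
- **TEA failure is also miscounted.** Counting failure by assigned arm is a legitimate measure of the TEA strategy, and the 4.2.2 switches are among those failures. The objection to assigned-arm counting reaches catheter complications only.

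It can also be said that an epidural complication in the IVPCA column identifies itself, since it can come only from a crossover catheter. That is true of the event count. It supplies no denominator of crossover catheters, and it does not bring the event into the rate per catheter.

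**Conclusion.** The point holds in a limited form. Followed as written, 8.2 tabulates a crossover-catheter complication under IVPCA, which is the wrong attribution for a harm specific to the catheter. The TEA denominator for epidural complications is undefined between about 105 and up to 150.

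Under the assumptions in step 5, misattribution involves about 0 to 2 events and 0 to 0.9 points on the TEA rate. If the evaluable set were used, the loss of precision is a zero-event one-sided upper limit of 2.8% rather than as low as 2.0%. The 2.0% assumes that all 150 had a catheter placed or attempted. Complication rates, crossover shares and the exposed fraction of the 45 are assumptions, because the documents give none. The direction of any bias is unknown, and the power calculation is unaffected. The change is still worth making, because epidural risk is part of the hypothesis, a listed endpoint and a reason for the 3:1 ratio.

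**What to change.** In 8.2:

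1. Exempt epidural complications from the blanket intent-to-treat sentence. Report them in every patient in whom a catheter was placed or attempted, whatever the assigned arm, resectability or questionnaire status.
2. Show postoperative crossover catheters as a separate row or column, beside the intent-to-treat comparison.
3. State that evaluable status applies only to pain and questionnaire endpoints.
4. Keep TEA failure by assigned arm.

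In section 10, state that the DSMB safety tables use the by-receipt set for epidural complications.

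The cost is wording and one extra table, with no extra patients or visits and no change to the sample size. This presumes that complications of crossover catheters are recorded in the same way as those of preoperative ones, which the TEA-only label in 6.1 leaves unclear.

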 - c. Only push entire dose of **Naloxone 0.4 mg** for respiratory arrest or continued hypoxia.
2. **Ondansetron 4 mg** IV every **6** hours prn nausea/vomiting. Notify ordering service if patient has no relief.
3. **Nalbuphine 5 mg** subcutaneous every **4** hours **2.5 mg** IV every **4** hours prn pruitus. Notify ordering service if patient has no relief.

Instructions/Education _____

Signature/Credentials/ID Code: _____

Pager: _____ Date: **11/22/2010** Time: **10:40 AM**

File under: Physician Orders

Page 1 of 1

INS 00004 V21 11/10/2010

Copyright 2010 The University of Texas M.D. Anderson Cancer Center

1. Administer **Naloxone (Narcan®)** as follows if patient does not respond to stimuli or continues to deteriorate as indicated under Interventions.
 - a. Dilute an ampule of **Naloxone 0.4 mg** in 9 mL NS for injection. Final Concentration: 0.04 mg/mL.
 - b. Inject **0.5 mL of diluted Naloxone** IV Push of diluted Naloxone every 2 minutes until respiratory rate is greater than 8 per minute and/or drowsiness abates.
 - c. Only push entire dose of **Naloxone 0.4 mg** for respiratory arrest or continued hypoxia.
2. **Ondansetron 4 mg** IV every 6 hours prn for nausea/vomiting.
3. **Nalbuphine 5 mg subcutaneously** every 4 hours prn pruritis.

[figure not shown]
HYDROMorphone _____ mg IV every 2 hours prn breakthrough pain. (Only administer if box checked by prescriber.)

Signature/Credentials/ID Code: _____
Pager: _____ Date: 11/22/2010 Time: 10:40 AM

Appendix C: Motor Block Scale

Bromage Motor Block Scale (0/5 complete motor block; 5/5 no motor block)	Right Leg	Left Leg
Hip Flexion	0 - 5	0 - 5
Knee Extension	0 - 5	0 - 5
Ankle Dorsiflexion	0 - 5	0 - 5
Ankle Plantar Flexion	0 - 5	0 - 5
Great Toe Dorsiflexion	0 - 5	0 - 5

Appendix D: Dermatome Sensory Block Map

Appendix E: Richmond Agitation Symptom Scale

+4	Combative	Violent, immediate danger to self or staff
+3	Very Agitated	Pulls or removes tube(s) or catheter(s); aggressive behavior
+2	Agitated	Frequent non-purposeful movement, fights ventilator
+1	Restless	Anxious, apprehensive but movements not aggressive or vigorous
0	Alert & Calm	
-1	Drowsy	Not fully alert, but has sustained awakening to voice (eye opening & contact > sec)
-2	Light Sedation	Briefly awakens to voice (eye opening & contact < 10 sec)
-3	Moderate Sedation	Movement or eye-opening to voice (but no eye contact)
-4	Deep Sedation	No response to voice, but movement or eye opening to physical stimulation
-5	Unarousable	No response to voice or physical stimulation

Appendix F: Numeric/Visual Analog Pain Scale
